Utilizing All Health System Contacts to Offer Postpartum Family Planning (PPFP) to Pregnant Women and Women within Twelve Months Postpartum in Ethiopia

Study Protocol

Jhpiego

Unique Protocol ID: IRB00007143

February 2, 2018

JHSPH IRB Research Plan for New Data Collection

PI Name: [name]
Study Title: Utilizing All Health System Contacts to Offer Postpartum Family Planning (PPFP) to Pregnant Women and Women within Twelve Months Postpartum in Ethiopia
IRB No: IRB00007143
PI Version No./Date: V3_February 2, 2018

I. Aims of the Study: Describe the aims/objectives of the research and/or the project's research questions or hypotheses.

The objectives and sub-objectives of this study are to:

- 1) Assess the effect of contacts that women/couples have with the health system (from the *kebele* [sub-district] level to the health facility level and back), into which postpartum family planning (PPFP) messages are systematically integrated, on uptake of PPFP through 12 months postpartum in Ethiopia. These health contacts span several levels: at health facilities from trained health professionals, and at community settings from Health Extension Workers (HEWs) and Health Development Army (HDA), a cadre of community volunteers.
 - a. Assess the extent and type of existing contacts that women/couples have with the health system during pregnancy, birth, and in the postpartum period and the degree to which they receive PPFP messages during these health contacts.
 - b. Assess the relationship between frequency and type of contact to uptake of PPFP and recommended child feeding and immunization practices (estimate the dose-response effect of each additional health contact).
- 2) Estimate the added effect of a community-based intervention (i.e. beyond the health center) to promote PPFP messaging at antenatal and postpartum contact points by community health workers (HEWs, HDA) on uptake of postpartum family planning through twelve months postpartum in two clusters of health center and health posts, as compared to health center-only PPFP counseling and services in two comparison clusters.
 - a. Measure "baseline" PPFP uptake through recall of women with prior birth history and their PPFP use after those recall births (sub-sample of women with prior birth history)
 - b. Prospectively assess uptake of PPFP among postpartum women by type of health contact, timing postpartum, and contraceptive method

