The Ethiopian health system envisages that a number of health contacts should occur for women and babies from pregnancy through to the extended postpartum. Figure 1 below illustrates these contacts.

Figure 1: Possible Contacts with the Health System for Pregnant Women in Ethiopia

Month	4	5	6	7	8	9		1	2	3	4	5	6
Client	Pregnancy						Birth	Postpartum Period					
HDA	x	x	x	x	x	X	Home	X	x	x	x	x	x
HEW	Quarterly visits: 2-3 times during last two trimesters of pregnancy							Quarterly visits: 2-3 times during first 12 months postpartum					
HC	ANC1 Before end of 4 th month		ANC2 24-28 weeks	ANC3 32 weeks	ANC4 36 weeks	Facility		PNC w/in 48 hours; w/in 6 weeks					
								DPT1 6 weeks		DPT2 10-14 weeks		DPT3 14-22 weeks	

About 84% infants receive at least one dose and more than 60% receive two doses of basic vaccines. A substantial number of mothers also seek care for their child's fever, diarrhea and other illness from health providers. This study will take these contact occasions as opportunities for promoting PFP, but also to reinforce the need to fully vaccinate children.

III. Study Design

- A. Provide an overview of your study design and methods. The study design must relate to your stated aims/objectives. Details will be requested later. If your study also involves analysis of existing data, please complete Section XI, "Secondary Data Analysis of Existing Data" in the last part of this research plan. If your study ONLY involves analysis of existing data, please use the research plan template for secondary data analysis (JHSPH IRB Research Plan for Secondary Data Analysis of Existing Data/Specimens).

This implementation research will use a quasi-experimental mixed method design with two arms. The intervention arm will have integrated PFP messages at each level of health system contacts. The control arm will continue to deliver the existing FP services at primary health care centers only.

The primary study population is a cohort of pregnant women, enrolled between the 2nd and 3rd trimester of pregnancy in both arms, who will be followed to twelve months post-partum. We will interview the women at study enrollment and at the end of the study. We will track women's contacts with the health system, particularly regarding PFP counseling, decision making and contraceptive adoption, through chart reviews of routinely collected facility and community based health records and registers (e.g. family folders that may be modified for study).

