#### A. Quantitative interviews with Women:

After data have been thoroughly examined for quality, the study team will perform exploratory data analysis of key variables such as checking frequency distributions, measures of variability, central tendency, and data outliers. We will also check for incomplete data and consider strategies to handle missing values such as undertaking an imputation strategy and weighting adjustments for non-responses.

We will compare differences by study arm for key variables. Analysis will account for clustering of variables at kebele (village) level using the Taylor linearization method. Differences between the arms for categorical variables will be assessed using the Pearson chi-squared test with the Rao-Scott correction. Differences in continuous variables will be assessed using an adjusted t-test. In case of substantial differences between the study arms, we will perform propensity score matching and perform the analysis with inverse probability weights.

Key descriptive variables:

- Sociodemographic data such as age, marital status, education, and socioeconomic status (nationally representative SES will be determined using the EquityTool described here: <http://www.equitytool.org/>)
- (Baseline only) Proportion of pregnant women with non-first pregnancies (non-primiparous) who previously used family planning
- Number of health system contacts where FP was discussed or provided, by type of contact (ANC, PNC, immunization, etc) and provider (facility provider, HEW, volunteer)
- Proportion of postpartum women who chose a method prior to delivery, by method, and received chosen method
- Proportion of postpartum women who used FP during the first 12 months after giving birth, by method
- Reasons for starting and stopping contraceptive methods and duration of use

- Initiation and duration of exclusive breastfeeding and lactational amenorrhea (LAM); average/median duration of postpartum amenorrhea, PP sexual initiation/PP abstinence
- Partner communication about family planning

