We will fit multivariable logistic regression models for the primary and secondary binary outcomes (see below) to examine differences between the study arms, adjusted for confounding covariates and clustering at kebele level. We will also conduct a “per-protocol analysis” by examining the “dose-effect” of health system contacts on the primary and secondary outcomes, regardless of study arm. We will run two dose-effect models, looking at the association between the outcomes and 1) the total number of contacts and 2) the number of contacts during which FP was discussed as reported by the woman. For the secondary outcome, we will only include contacts during pregnancy since contacts after the birth would not have a temporal effect on whether the woman chose a method prior to delivery.

- Primary outcome:
  - Proportion of interviewed postpartum women who used a modern family planning method within 12 months after giving birth
- Secondary outcome:
  - Proportion of interviewed postpartum women who chose a method prior to delivery

We will also conduct time-to-event analyses using life-table method and use a log-rank test to test for differences in survival distributions between the study arms in terms of the timing of FP uptake after birth. We will perform multivariable hazards model (Cox’s proportional model or parametric model with Weibull distribution in case of non-normality in hazards function) for adjusting confounding covariates and clustering effects.

Additionally, we will run hazards regression models for women who initiated exclusive breastfeeding/LAM after birth to test for differences between arms in the duration of exclusive breastfeeding/LAM use.

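### The type-of-contact half of Objective 1b has no model: both SAP dose-effect models use one pooled contact count

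*SAP*

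**What the plan says.** Protocol section I, Objective 1b, sets two tasks: "Assess the relationship between frequency and type of contact to uptake of PPFP and recommended child feeding and immunization practices". A parenthesis adds that the dose-response effect of each further contact is to be estimated. Objective 1 describes contacts as occurring "at health facilities from trained health professionals, and at community settings from Health Extension Workers (HEWs) and Health Development Army (HDA" volunteers). Objective 2b again asks for uptake by type of contact.

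The SAP's second objective describes the dose-response analysis by number of contacts only. SAP section A then names the two dose variables: "We will run two dose-effect models, looking at the association between the outcomes and 1) the total number of contacts and 2) the number"; the second count is limited to contacts where the woman reports FP discussion. Both models combine the arms. The only restriction on which contacts count is one of timing: pregnancy contacts only for the secondary outcome.

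Contact type appears elsewhere in the SAP under key descriptive variables: "Number of health system contacts where FP was discussed or provided, by type of contact (ANC, PNC, immunization, etc) and provider". The protocol's analysis list (section V.C, item 4) has the share of ANC and PNC contacts with FP discussed, split by HDA, HEW and health-centre worker and compared by arm. Neither item is linked to uptake. SAP section C brings stock-outs and counselling quality into the per-protocol analyses, but not contact type.

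**The concern.** A single count forces one coefficient on a volunteer's home visit, an HEW visit, an ANC visit and a facility birth. If these differ in effect, the slope describes none of them. A reader who takes the result as the effect of one more contact could not tell which kind of contact to expand, and that is what the type half of Objective 1b is meant to inform.

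The contacts also differ by arm in content. Protocol section III.A says that HEWs get the additional training in PPFP messaging in the intervention site only, and that they then train the HDAs there. Combining the arms without an arm term therefore mixes community contacts of different content.

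**Working it through.** **The plan's own figure.** The documents give no figure for the dose-effect models. Their sample size concerns the arm comparison and reproduces: for 20% vs 10%, two-sided 0.05 and 80% power, n = 198.96; times 1.5 = 298.4, so 299 per arm. It is not in dispute.

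**What a pooled slope estimates.** Let T be the sum of the type-specific counts X_k with log odds ratios β_k. To a linear approximation, pooled log OR = Σ w_k β_k, with w_k = Cov(X_k, T) / Var(T). If the counts are independent, w_k = Var(X_k) / Σ Var(X_j).

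**Counts from protocol Figure 1.** HDA: 6 + 6 = 12. HEW: 2-3 in pregnancy ("Quarterly visits: 2-3 times during last two trimesters of pregnancy") plus 2-3 postpartum = 4-6; 5 is used. Health centre: 4 ANC + 1 birth + 2 PNC + 3 DPT = 10. The windows are not identical: HDA marks stop at month 6, while HEW visits run to 12 months.

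**Assumed truth (not in the documents).** OR 1.30 per facility contact, log OR 0.262; OR 1.00 per HEW or HDA contact.

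*Scenario A: every contact attended independently with probability 0.5.*
- Variances: HDA 12 × 0.25 = 3.00; HEW 5 × 0.25 = 1.25; facility 10 × 0.25 = 2.50; total 6.75.
- Weights: 44%, 19%, 37%.
- Pooled OR = exp(0.37 × 0.262) = 1.10. A logistic simulation of one million women also gives 1.10, or 36% of the facility log OR.

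*Scenario B: facility attendance from protocol section II; HDA and HEW still at 0.5.*
- ANC: 43% any and 19% four visits. The other 24% is assumed spread evenly over 1, 2 and 3 visits (8% each). Mean 0.08 × 6 + 0.19 × 4 = 1.24; variance 0.08 × 14 + 0.19 × 16 − 1.24² = 2.62.
- Birth: 89.5% at home, so 0.105 × 0.895 = 0.09.
- PNC: 6.7% assumed for each of two visits, so 2 × 0.067 × 0.933 = 0.13.
- DPT: first dose 80.0%, third 65.7%, doses nested, second assumed midway at 72.85%. Mean 2.1855; variance 0.0715 × 1 + 0.0715 × 4 + 0.657 × 9 − 2.1855² = 1.49.
- Facility variance 2.62 + 0.09 + 0.13 + 1.49 = 4.33; total with 3.00 and 1.25 = 8.58.
- Weights: HDA 35%, HEW 15%, facility about 51%.
- Pooled OR = exp(0.505 × 0.262) = 1.14. Logistic simulations give 1.14 to 1.15, depending on details the documents leave open.

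**Correlated contacts.** With facility OR 1.25, mean counts of 6 facility, 3 HEW and 3, 6 or 12 HDA, and latent correlation 0, 0.3 or 0.6 (all assumed), the pooled OR ranged from 1.03 to 1.12. Separate counts returned about 1.25, 1.00 and 1.00 in all nine scenarios.

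**Price of separating.** Under scenario A, with about 600 women (2 × 299), 15% uptake and no design effect, the standard error of the log OR is 0.044 for the pooled slope. It is 0.066 for HDA, 0.103 for HEW and 0.074 for facility.

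**The case against.** The strongest reply has several parts, and much of it stands.

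A reader might infer that the dose models cannot answer Objective 1b at all. The documents do not support that: a total-count slope is a direct estimate for the part of 1b about each additional contact. Only the type half is without a model.

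A reader might also infer that the study then cannot say whether community work adds anything beyond the health centre. That question belongs to protocol Objective 2 and the SAP's first objective, and the arm comparison answers it. Pooling contacts in the dose models does not touch that estimate.

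Nor does the SAP say that the slope will be read as a volunteer-visit effect. It speaks of association and does not define the total by provider. That HDA visits are in the total is inferred from the protocol's description of contacts; nothing in the SAP excludes them. If all types had equal effects, the pooled slope would be right.

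The protocol does have partial breakdowns: method choice before delivery by number of ANC contacts, and uptake by postpartum service point. Both are descriptive, and neither isolates HEW or HDA contacts. The second SAP model drops contacts without FP discussion but still pools providers.

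Finally, the size depends on assumed attendance, as the two scenarios show. Neither represents the second model or the pregnancy-only count for the secondary outcome. The direction survives; no single percentage does.

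**Conclusion.** The point holds in a limited form. As written, the plan answers the frequency half of Objective 1b and leaves the type half without any model of uptake. Where contact types differ in effect, the pooled slope blends them: with a facility-only effect of OR 1.30, it would be about 1.10 under uniform 0.5 attendance and about 1.14 to 1.15 under the protocol's facility coverage. These figures show the mechanism and are not forecasts, because the documents give no type-specific effects and no HDA or HEW attendance. The primary comparison is unaffected. The change is still worth making before analysis, because a stated objective lacks a model and one can be added cheaply.

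**What to change.** Keep both total-count models as the answer on frequency. Beside each, add a model in which three counts enter together: facility provider, HEW, and HDA/volunteer. Include a study-arm term, and keep the confounder adjustment and kebele-level clustering already planned. Report an OR with CI per additional contact of each type, and a test that the three ORs are equal. For the secondary outcome, count pregnancy contacts only, as the SAP already requires.

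The provider split is documented for contacts with FP discussed (SAP section A, key descriptive variables). It should not be presumed for total contacts. There, use the split that the women's questionnaire supports; protocol Table 1 lists ANC visits, place of delivery, PNC at facility or home, and immunization visits. State in the SAP which contacts make up each count.

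The cost is SAP wording, two more contact coefficients per added model plus the arm term, and wider intervals per type than for the pooled slope. Separating the counts does not remove confounding by care-seeking, so the results remain observational associations. Three provider counts also still average over ANC, birth, PNC and immunization within facility contacts.

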- 3) Explore acceptability and feasibility among HC providers and health extension workers of using record keeping and review processes to track women's decision-making and contraceptive use from pregnancy through to 12 months postpartum,
 - a. Test provider/health extension worker (HEW)/health development army (HDA) use of health record keeping systems as a tool for identifying women who need additional PPFP counseling (prenatal).
 - b. Test use of a monthly data review process to combine HEW and HDA health records of pregnant and recently delivered women and their babies to ensure maximum coverage of critical health practices including antenatal care (ANC), postnatal care (PNC) home visits, PPFP uptake, immunization, infant feeding, etc.
- 4) Explore factors influencing women's/couples' adoption of PPFP during the first twelve months postpartum.

In both intervention and comparison sites, the study will implement the current Government of Ethiopia policy and standard of care concerning systematic integration of PPFP messages and services within antenatal care, labor and

delivery, postnatal care as well as a new proposed targeting of women bringing infants for immunization services with PFP messages and referrals.

II. Background and Rationale: Explain why this study is being done. Summarize briefly what is already known about the issue and reference previously published research, if relevant.

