Prior to study implementation, we will conduct a readiness assessment of selected health facilities in both study arms to ensure that the supplies, equipment and commodities are available for PFP counseling and service delivery capacity in all health centers. Gaps in PFP service delivery will be addressed in both intervention and control study sites. Health center maternity staff will be trained in PFP (PFP counseling, postpartum IUD and implant provision, etc.) in accordance with current Government of Ethiopia PFP expansion strategies. The rapid assessment will provide an understanding of service delivery capacity and needs and allow MCSP to ensure the same services and equipment are available in all sites.

[figure not shown]
In intervention sites, both facility-based providers at primary health center and health post levels, including HEW and HDAs, will receive training on PFP counseling and use of adapted health records. Should HEW require refresher training in implant provision or other methods, the study will also provide this.

In addition, we will conduct a rapid formative assessment to understand the health system and cultural contexts of PFP needs during the preparatory phase of intervention implementation. This formative study will include household members of pregnant women, community health workers (HDAs), and facility-based providers, including HEWs, and managers. This rapid assessment will support the design of the intervention at the community level which will include designing and training HEWs to communicate PFP messages as part of a bundle of messages that promotes high impact maternal, newborn, and child health (MNCH) practices and care-seeking behavior. HEWs at health posts in the intervention site only will receive additional training on tracking clients and providing PFP messaging (as well as other FP/implant refresher as needed) at routine antenatal and postpartum contacts. HEWs in the intervention site will train HDAs on these messages and will receive job aids and tracking tools for PFP messaging. Data from chart reviews and review of health records in the intervention and control arms will be analyzed to determine differences in PFP counselling, decision-making on method choice, and uptake of PFP by study arm.

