## Analysis Plan

### Utilizing All Health System Contacts to Offer Postpartum Family Planning (PPFP) to Pregnant Women and Women within Twelve Months Postpartum in Ethiopia

This plan describes how data collected through different methods will be analyzed after cleaning in order to meet these research objectives:

1. Estimate the added effect of the community-based intervention by comparing uptake of PPFP through 12 months postpartum in intervention and comparison sites (“intent to treat” analysis)
2. Assess the effect of systematically integrating PPFP messages into contacts with the health system on uptake of PPFP through 12 months postpartum using a dose-response analysis based on the number of contacts (“per protocol” analysis)
3. Explore the feasibility of tracking PPFP and reviewing data at health centers and HEWs and volunteers using record keeping and review processes to track women's decision-making and contraceptive use from pregnancy through 12 months postpartum
4. Explore factors influencing women's/couples' adoption of PPFP during the first 12 months postpartum

Quantitative and qualitative data analysis will be triangulated to help interpret results and provide deeper insights on study objectives.

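### The two separate dose models planned for SAP objective 2 cannot tell exposure to family planning messages from how often a woman attends, and for the primary outcome they do not exclude contacts at or after uptake

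*SAP*

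**What the plan says.** SAP objective 2 is worded causally: "Assess the effect of systematically integrating PPFP messages into contacts with the health system on uptake of PPFP through 12 months postpartum". The means given is "using a dose-response analysis based on the number of contacts".

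SAP section A describes that analysis. It ignores arm and consists of two models, with exposures "1) the total number of contacts and 2) the number of contacts during which FP was discussed as reported by the woman". No model contains both counts. The paragraph opens with multivariable logistic models for the arm comparison, adjusted for unnamed confounders and for kebele clustering; it does not say whether this adjustment carries over to the dose models. Contacts are limited to pregnancy for the secondary outcome (method chosen before delivery). No timing limit is given for the primary outcome (modern method use within 12 months of birth). SAP section C adds stock-outs and counselling quality to the per-protocol analyses.

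On what differs between arms, Protocol section I states: "In both intervention and comparison sites, the study will implement the current Government of Ethiopia policy and standard of care concerning systematic integration". Section III.A says that gaps in service delivery "will be addressed in both intervention and control study sites", and the end of section III.B says that all health centres in the woreda get the same strengthening. The difference is at community level: "HEWs at health posts in the intervention site only will receive additional training on tracking clients". An earlier sentence of section III.A reads otherwise: "The control arm will continue to deliver the existing FP services at primary health care centers only".

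**The concern.** With facility-level integration in both arms, the arm contrast estimates the added community component, which is SAP objective 1. Objective 2 then has to be answered within the pooled cohort, where the informative comparison is between contacts with an FP message and contacts without one. Neither model makes it. The first counts every contact whether or not FP was raised. The second counts FP-discussed contacts without holding the number of contacts fixed, so a frequent attender tends to get a higher dose simply by attending.

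Women who attend more may also be readier to use contraception. If so, a positive slope in either model could be read as evidence that the messages work when it reflects attendance. Pooling without arm also lets any arm or site difference in uptake enter the slope.

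**Working it through.** **The plan's own figures.** Protocol section III.B gives p1 = 0.20, p2 = 0.10, two-sided alpha 0.05, power 80%, design effect 1.5 and 20% loss. With mean p = 0.15:

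n = [1.96 × √(2 × 0.15 × 0.85) + 0.8416 × √(0.20 × 0.80 + 0.10 × 0.90)]² / 0.10² = 198.96 per arm.

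198.96 × 1.5 = 298.4, so 299; 299 / 0.8 = 373.75, so 374 against the stated 375. The figures reproduce, but they concern the arm comparison. The documents give no sample size or power for the dose models, and no figure for the link between care-seeking and uptake.

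**Mechanism.** Let C be total contacts, F the FP-discussed contacts and q the share of contacts with discussion. If discussion is unrelated to the woman, E(F | C) = qC. Anything that raises both C and uptake therefore gives F a slope. Holding C fixed removes that route.

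**Illustration with no message effect.** All inputs are assumed except the number of women, 598 = 2 × 299, and uptake of about 15%, the midpoint of the planned 20% and 10%. A care-seeking trait U is standard normal; C is Poisson with mean 6 × exp(0.4U − 0.08); F is binomial(C, q) with q = 0.3, 0.5 or 0.7; logit P(uptake) = logit(0.15) + bU. Plain logistic fits, no covariates or clustering, 400 runs per setting. Cells show the range over q of the odds ratio (OR) per contact and of the share of runs with p < 0.05.

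| b (uptake OR per SD, e^b) | Total contacts alone | FP-discussed alone | FP-discussed, total in model |
|---|---|---|---|
| 0 (1.00) | 0.997–0.998; 2–6% | 0.994–0.996; 4–7% | 0.996–1.003; 5–7% |
| 0.2 (1.22) | 1.037–1.039; 20–27% | 1.045–1.063; 14–20% | 0.998–1.005; 4–7% |
| 0.4 (1.49) | 1.077–1.078; 67–70% | 1.092–1.119; 37–60% | 0.991–0.999; 3–6% |
| 0.7 (2.01) | 1.132–1.136; 98–99% | 1.157–1.214; 81–95% | 0.993–1.001; 4–7% |

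At a true 5% rate the simulation error is √(0.05 × 0.95 / 400) = 1.1 percentage points, so 3–7% is compatible with 5%.

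A second set-up used 600 women, discussion at 30% of control and 45% of intervention contacts, and 300 runs per setting. Over repeat runs at b = 0.25, 0.5 and 0.75, the FP-discussed model was significant in 20–24%, 70–74% and 94%. With total contacts and arm added, the rate was 4–7%.

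**Limits of the joint model, still with no message effect.** The last column depends on discussion being random given contacts. Relaxing that:
- In the first set-up, the care-seeking trait also raises the share of contacts with discussion (0.5 log-odds per SD, b = 0.4, q = 0.5): joint OR 1.08, 15% significant; FP-discussed alone OR 1.10, 78%.
- In the second set-up, a separate interest trait raises both discussion and uptake (0.5 log-odds per SD each, b = 0.5): joint OR with arm about 1.17, about 60% significant.
- In the second set-up, each adopter gains one FP-discussed contact on obtaining the method (b = 0.25): joint OR with arm 1.42, 99% significant; FP-discussed alone OR 1.33. If half of adopters gain one, the joint OR is 1.20, 58% significant.

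The last case matters because SAP section A describes contacts at which FP was discussed or provided, and sets no timing limit for the primary outcome. Holding total contacts fixed does not cure it; in this setting the joint model is further from 1 than the SAP's own.

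**The case against.** **The SAP speaks of association, and no bias is shown.** This largely stands. A reader might infer that the SAP will report care-seeking as an effect of the messages, or that both models will show a gradient whatever the truth. The documents do not support either. The model description uses the language of association; causal wording comes from the objective and from the label given to the dose analysis. With b = 0 the separate models keep about a 5% error rate.

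**Covariate adjustment may carry over.** It may: the dose models follow directly on the adjusted arm models, and age, education, socioeconomic status and past FP use are collected. Adjustment helps only as far as the covariates capture care-seeking. In the second set-up at b = 0.5, a measured covariate correlated 0.3, 0.5 or 0.7 with the trait left the FP-discussed model significant in 64%, 52% and 29% of runs; the joint model with arm gave 6%, 9% and 3%. Stock-outs and counselling quality do not measure a woman's care-seeking.

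**The total-contacts model is deliberate.** This stands. Protocol aim 1b asks about each additional health contact, and that model addresses it. It cannot also be evidence about messages.

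**The joint model is no clean answer, and adding arm is debatable.** Both stand. Arm is the source of variation in FP discussion least tied to a woman's own interest, so conditioning on it leaves mostly self-selected variation. In the adopter-contact runs, adding arm moved the joint OR from 1.36 to 1.42. Leaving arm out, however, lets arm and site differences into the slope.

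**Conclusion.** The concern holds in a limited form. As specified, neither dose model can separate exposure to messages from frequency of attendance, and objective 2 calls the result an effect. If care-seeking also predicts uptake, either model could show a dose-response with no message effect. How large this would be in the trial is unknown: the simulated rates rest on assumed contact numbers, discussion shares and strength of confounding, and leave out clustering and, except where stated, covariates.

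It would be tempting to conclude that putting both counts in one model gives the answer to objective 2. The checks do not support that. The joint model removes the attendance route only. It stays biased if a woman's interest prompts the discussion, and can do worse than the SAP's model if the contact that supplies the method is counted. Pre-uptake timing is therefore as necessary as the joint fit.

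The Protocol section III.A sentence describing the control arm as existing services is a secondary point. It sits badly with sections I and III.B and with the rest of III.A, although SAP objective 1 already frames the arm contrast as the added community effect.

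**What to change.** In SAP section A:

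1. Keep the total-contacts model for protocol aim 1b and label it an association with contact frequency.
2. For objective 2, fit FP-discussed and total contacts in one model (equivalently, FP-discussed and non-FP contacts), with the confounding covariates and kebele clustering already planned for the arm models. Name the covariates. Show the model with and without study arm.
3. For the primary outcome, count only contacts before method uptake. Two routes fit the existing plan: the antenatal counts already used for the secondary outcome, or time-varying contacts in the planned hazards model, which needs contacts that can be dated relative to uptake.
4. Report the FP-discussed coefficient as an adjusted association, and say that discussion is self-reported and may follow a woman's own interest.

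Separately, reconcile the control-arm sentence in Protocol section III.A with sections I and III.B and the rest of III.A.

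The cost is mainly wording, since both counts are already needed for the planned models. The FP-discussed coefficient will have a wider interval because the two counts are correlated, and fewer contacts will be counted. If only antenatal counts are used, postnatal and immunization contacts drop out of that analysis and the question it answers is narrower.
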